### 10.4.2. Male Subjects

If a female partner of a male subject taking study treatment (durvalumab, subcutaneous azacitidine) becomes pregnant while the male subject is on IP, or within 90 days of the male subject's last dose of IP, the male subject taking study treatment (durvalumab, subcutaneous

azacitidine) should notify the Investigator, and the pregnant female partner should be advised to call their healthcare provider immediately.

## 10.5. Reporting of Serious Adverse Events

Any AE that meets any criterion for an SAE requires the completion of an SAE Report Form in addition to being recorded on the AE page/screen of the eCRF. All SAEs must be reported to Celgene Drug Safety within 24 hours of the Investigator's knowledge of the event by facsimile, or other appropriate method (eg, via email), using the SAE Report Form, or approved equivalent form. This instruction pertains to initial SAE reports as well as any follow-up reports.

The Investigator is required to ensure that the data on these forms is accurate and consistent. This requirement applies to all SAEs (regardless of relationship to study treatment (durvalumab, subcutaneous azacitidine) that occur during the study (from the time the subject signs informed consent form until 28 days after the last dose of subcutaneous azacitidine (90 days after the last dose of durvalumab), whichever is later or any transformation to AML cases (MDS subjects) and those SAE made known to the Investigator at any time thereafter that are suspected of being related to study treatment (durvalumab, subcutaneous azacitidine). Serious adverse events occurring prior to treatment (after signing the ICF) will be captured.

The SAE report should provide a detailed description of the SAE and include a concise summary of hospital records and other relevant documents. If a subject died and an autopsy has been performed, copies of the autopsy report and death certificate are to be sent to Celgene Drug Safety as soon as these become available. Any follow-up data should be detailed in a subsequent SAE Report Form, or approved equivalent form, and sent to Celgene Drug Safety.

Where required by local legislation, the Investigator is responsible for informing the Institutional Review Board/Ethics Committee (IRB/EC) of the SAE and providing them with all relevant initial and follow-up information about the event. The Investigator must keep copies of all SAE information on file including correspondence with Celgene and the IRB/EC.

### 10.5.1. Safety Queries

Queries pertaining to SAEs will be communicated from Celgene Drug Safety to the site via facsimile or electronic mail. The response time is expected to be no more than five (5) business days. Urgent queries (eg, missing causality assessment) may be handled by phone.

## 10.6. Expedited Reporting of Adverse Events

For the purpose of regulatory reporting, Celgene Drug Safety will determine the expectedness of events suspected of being related to durvalumab and subcutaneous azacitidine based on the Investigator's Brochures.

In the United States, all suspected unexpected serious adverse reactions (SUSARs) will be reported in an expedited manner in accordance with 21 CFR 312.32.

For countries within the European Economic Area (EEA), Celgene or its authorized representative will report in an expedited manner to Regulatory Authorities and Ethics Committees concerned, SUSARs in accordance with Directive 2001/20/EC and the Detailed Guidance on collection, verification and presentation of adverse reaction reports arising from

clinical trials on investigational products for human use (ENTR/CT3) and also in accordance with country-specific requirements.

Adverse events such as death related to disease progression (in the absence of serious IP-related events) and serious events due to the relapse of the studied indication will not be subject to expedited reporting by the sponsor to regulatory authorities. These events will be captured as AEs on the eCRF, reported to Celgene Drug Safety if meeting SAE reporting criteria (within 24 hours) and reported to regulatory authorities in the annual report.

Celgene or its authorized representative shall notify the Investigator of the following information:

- Any AE suspected of being related to the use of study treatment (durvalumab, subcutaneous azacitidine) in this study or in other studies that is both serious and unexpected (ie, SUSAR);
- Any finding from tests in laboratory animals that suggests a significant risk for human subjects including reports of mutagenicity, teratogenicity, or carcinogenicity.

Where required by local legislation, the Investigator shall notify his/her IRB/EC promptly of these new serious and unexpected AE(s) or significant risks to subjects.

The Investigator must keep copies of all pertinent safety information on file including correspondence with Celgene and the IRB/EC (see Section 14.3 for record retention information).

#### **Celgene Drug Safety Contact Information:**

For Celgene Drug Safety contact information, please refer to the Serious Adverse Event Report Form Completion Guidelines or to the Pregnancy Report Form Completion Guidelines.

### **10.7. Adverse Events of Special Interest**

An Adverse event of special interest (AESI) is one of scientific and medical interest specific to understanding of the Investigational Product and may require close monitoring and rapid communication by the Investigator to the sponsor. An AESI may be serious or nonserious. The rapid reporting of AESIs allows ongoing surveillance of these events in order to characterize and understand them in association with the use of this investigational product.

Adverse events of special interest for durvalumab include but are not limited to events with a potential inflammatory or immune-mediated mechanism, and which may require more frequent monitoring and/or interventions such as steroids, immunosuppressants and/or hormone replacement therapy. These AESIs are being closely monitored in clinical studies with durvalumab monotherapy and combination therapy. An imAE is defined as an adverse event that is associated with drug exposure and is consistent with an immune-mediated mechanism of action and where there is no clear alternate aetiology. Serologic, immunologic, and histologic (biopsy) data, as appropriate, should be used to support an imAE diagnosis. Appropriate efforts should be made to rule out neoplastic, infectious, metabolic, toxin, or other etiologic causes of the imAE.

If the Investigator has any questions in regards to an AE being an imAE, the Investigator should promptly contact the Medical Monitor.

Further information on risks (eg, presenting symptoms) can be found in the current version of the Investigator Brochure including guidelines for their evaluation and treatment.

**10.7.1. Transformation to AML (for MDS Cohort only)**

Transformation to AML will be monitored as an AESI and must be reported as an SAE regardless of causal relationship to IP, occurring at any time for the duration of the study, from the time of signing the ICF until death, lost to follow-up, withdrawal of consent for further data collection, or study closure, whichever is later.

CELGENE PROPRIETARY INFORMATION

## 11. DISCONTINUATIONS

### 11.1. Treatment Discontinuation

The following events are considered sufficient reasons for discontinuing a subject from the investigational product(s):

- Adverse Event
- Progressive disease
- Withdrawal by subject
- Death
- Lost to follow-up
- Pregnancy
- Other (to be specified on the eCRF).

The reason for discontinuation of treatment should be recorded in the eCRF and in the source documents.

The decision to discontinue a subject from treatment remains the responsibility of the treating physician, which will not be delayed or refused by the sponsor. However, prior to discontinuing a subject, the Investigator may contact the sponsor's medical monitor and forward appropriate supporting documents for review and discussion.

### 11.2. Study Discontinuation

The following events are considered sufficient reasons for discontinuing a subject from the study:

- Screen failure
- Adverse event
- Withdrawal by subject
- Death
- Lost to follow-up
- Study Closure
- Other (to be specified on the eCRF).

The reason for study discontinuation should be recorded in the subject's eCRF and in the source documents.

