### 3.2.3.2. Survival Follow-up

After completing the Safety Follow-up Visit(s), subjects will be followed and contacted every 3 months until death, lost to follow-up, withdrawal of consent to further follow-up, or study closure to collect information related to:

- Survival,
- Subsequent MDS/AML-related therapies,
- Disease transformation to AML (for MDS subjects only).

This follow-up will continue until the last active subject completes at least 12 months of treatment and/or follow-up unless additional follow-up is needed to evaluate time-to-event endpoints (eg, progression-free survival [PFS] and survival). Follow-up contacts will be conducted every 3 months by telephone unless special circumstances exist (eg, the subject will visit the center for a nonstudy-related reason).

Females of childbearing potential should avoid becoming pregnant for 90 days after the last dose of IP and male subjects should avoid fathering a child for 90 days after the last dose of IP.

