### 3.2.4. Discontinuation from Study

The following events are considered sufficient reasons for study discontinuation:

- Withdrawal of consent
- Death
- Lost to follow-up
- Study closure
- Screen failure
- Other (to be specified on the eCRF).

Subjects not meeting one of these criteria will still be part of the survival follow-up.

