### 6.15. Follow-up

All subjects discontinued from treatment with IP for any reason will be followed for a period of at least 28 days after the last dose of subcutaneous azacitidine and 90 days after the last dose of durvalumab or until the date of the treatment discontinuation visit, whichever is later. During Safety Follow-up Visits, the following assessments will be performed:

- AEs including AESIs (monitored until 28 days after last dose of subcutaneous azacitidine or 90 days after last dose of durvalumab)
- physical examination
- vital signs
- body weight
- ECOG performance status
- hematology
- serum chemistry (to include amylase and lipase)
- thyroid function tests
- pregnancy testing (FCBP only)

- urinalysis
- concomitant medications, therapies and procedures
- transfusion assessment
- subsequent MDS/AML therapies
- survival

Females of childbearing potential should avoid becoming pregnant for at least 90 days after the last dose of IP and male subjects should avoid fathering a child for at least 90 days after the last dose of IP. The ICF will address any country-specific requirements, as needed.

All subjects discontinued from protocol-prescribed therapy for any reason will also be contacted by telephone every 3 months (12 weeks  $\pm$  14 days) following the Safety Follow-up Visit(s) until the last active subject reaches 12 months of treatment, unless additional follow-up is needed to evaluate time-to-event endpoints (eg, PFS and survival), or until death, lost to follow-up, withdrawal of consent to further follow-up, or study closure to collect information related to:

- survival
- subsequent MDS/AML therapies
- disease transformation to AML (only for MDS cohort subjects).

The Investigator must make every effort to obtain information regarding the subject's follow-up status. All attempts to contact the subject must be documented and appropriate due diligence must be demonstrated before the subject can be considered lost to follow-up (eg, 3 unsuccessful attempts by telephone and one unanswered written attempt sent by certified or traceable post).

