### 7.2.1.4. Missing Doses

Subjects will receive subcutaneous azacitidine 75 mg/m^2/day for 7 days every 28 days until the end of the study, unless they are discontinued from the treatment. In the event 2 or less doses are missed during the 7-day dosing period, dosing should continue so the subject receives the full 7 days of therapy. If 3 or more days are missed during the 7-day dosing period, the Investigator should contact the sponsor and a decision on dosing will be made on a case-by-case basis.

In order to optimally benefit from the azacitidine treatment, Investigators should aim to treat subjects for at least 6 cycles. However, subjects may be discontinued from the treatment per Investigator discretion, even during the first 6 cycles, for any of the reasons detailed in Section 11.1. If the dose of subcutaneous azacitidine is modified during the course of the study (Section 7.2.2.1) and benefit is demonstrated at a dose lower than 75 mg/m^2, that dose should be maintained during subsequent cycles that are given (unless toxicity develops). All subjects discontinued regardless of the reason will be followed for a period of 28 days following the date of the last dose of subcutaneous azacitidine or the date of the Treatment Discontinuation Visit (whichever date is later) for collection of AEs and will also be followed for survival until the end of the study.

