6. SUBJECT DISPOSITION

Reasons for screen failure will be summarized and listed. Enrollment by country and sites will be summarized by treatment arm within each disease cohort.

A summary of subject disposition (analysis population allocation, subjects randomized, subjects discontinued, along with primary reason for treatment discontinuation and study discontinuation) will be presented for the ITT Population and for the Safety Population and will be summarized using frequencies for both Treatment and Follow-up Periods.

Reasons for discontinuing study treatment will be collected on the CRF and will be summarized for all randomized subjects with the following categories:

- Completed
- Death
- Adverse event
- Progressive disease
- Lack of efficacy
- Withdrawal by subject
- Lost to follow-up
- Protocol violation
- Other

Reasons for discontinuing the study (ie, no follow-up visit and no longer participating in the study) will be collected on the CRF and will be summarized for all randomized subjects with the following categories:

- Completed (per protocol)
- Death
- Adverse event
- Withdrawal by subject
- Lost to follow-up
- Other

Protocol violations / deviations will be summarized and listed by disease cohort and treatment arm for the ITT Population. Protocol violation / deviation will be reported and monitored throughout the study. Data of protocol violation / deviation will be finalized prior to database lock.

The following by-subject listing of subjects with demographic information will be provided:

- Subject listing of discontinuation.

- Subject listing of screen failures.
- Subject listing of protocol violations and protocol deviations.
- Subject listing of being excluded from ITT, EE, Safety or PK Population.

CELGENE PROPRIETARY INFORMATION

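### Protocol 11.2 and SAP 6 list an adverse event as a reason for leaving the study, which contradicts Protocol 3.2.4 and the follow-up sections and could lead to informative censoring of overall survival at last contact

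*Protocol*

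**What the plan says.** Two protocol sections list the reasons for leaving the study, and the lists differ.

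- **Protocol 3.2.4**: "The following events are considered sufficient reasons for study discontinuation". It names withdrawal of consent, death, loss to follow-up, study closure, screen failure and other. It then adds: "Subjects not meeting one of these criteria will still be part of the survival follow-up". An adverse event is not named.
- **Protocol 11.2**: "The following events are considered sufficient reasons for discontinuing a subject from the study". It names screen failure, adverse event, withdrawal by subject, death, loss to follow-up, study closure and other.

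SAP 6 follows 11.2. It states "Reasons for discontinuing the study (ie, no follow-up visit and no longer participating in the study) will be collected on the CRF" and includes adverse event among six categories. Stopping treatment is handled separately, with its own adverse-event category in Protocol 11.1 and in the SAP 6 treatment list.

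The follow-up sections agree with 3.2.4:

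- **Protocol 3.2.3.2**: "subjects will be followed and contacted every 3 months until death, lost to follow-up, withdrawal of consent to further follow-up, or study closure".
- **Protocol 6.15**: "All subjects discontinued from protocol-prescribed therapy for any reason will also be contacted by telephone every 3 months". Protocol 6.7.7 has the same scope.
- **Protocol 7.2.1.4**, on subjects discontinued for whatever reason: "and will also be followed for survival until the end of the study".

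For OS, Protocol 9.6.1.2 and SAP 10.2 count death from any cause as the event. They censor other subjects at the date last known alive or at last contact. Neither has a rule for a subject who leaves the study because of an adverse event, and SAP 10.2 plans no OS sensitivity analysis for that case.

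**The concern.** The conflict lies in current text that sites act on. A site closing out a subject with a severe adverse event can cite 11.2, and the category list in SAP 6 indicates that the CRF offers a matching reason. SAP 6 describes that exit as the end of participation, so it cannot be read as stopping drug only. If the site acts on it, the telephone contacts on survival, subsequent therapy and AML transformation stop, although four other sections require them to continue.

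Kaplan-Meier estimates and the stratified log-rank test assume that censoring is unrelated to prognosis. Subjects who leave because of a severe adverse event are likely to have a higher risk of death than those who stay. Censoring them would make survival in their arm look better than it is. The treatment comparison is affected to the extent that such exits differ between arms. That is possible here, because treatment is open-label and only the combination arm is subject to the durvalumab discontinuation rules in Appendix M.

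**Working it through.** **Step 1: the texts side by side.**

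| Place | Does an adverse event end study participation? |
|---|---|
| Protocol 11.2 | Yes, it is a listed sufficient reason |
| SAP 6 | Recorded as an exit category, with no further visits or participation |
| Protocol 3.2.4 | Not listed; unlisted cases stay in survival follow-up |
| Protocol 3.2.3.2 | No; contacts end at death, loss, withdrawal of consent to follow-up, or closure |
| Protocol 6.7.7, 6.15, 7.2.1.4 | No; follow-up applies whatever the reason for stopping therapy |

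The first two rows cannot be reconciled with the rest.

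**Step 2: an illustration of size.** The plan states no figure to reproduce and no expected rate of exit for adverse events.

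Inputs from the protocol are the median OS on azacitidine: 10.4 months in older AML (1.3.3) and 24.46 months in higher-risk MDS (1.3.2). The assumptions, none of which is in the documents, are:

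- survival is exponential;
- a share f = 10% of one arm is due to exit at a time U, uniform on months 0 to 6, and does so if still alive;
- the death hazard is multiplied by k after exit;
- last contact falls c months after exit, and nothing is known of the subject afterwards.

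The hazard is λ = ln 2 / median, which is 0.0666 per month (AML) and 0.0283 (MDS). Without exits, 12-month survival is S = exp(−12λ) = 44.9% (AML) and 71.2% (MDS).

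True 12-month survival in the exit group is

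g = exp(−12kλ) × [exp(6(k−1)λ) − 1] / [6(k−1)λ].

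In AML with k = 2: 0.2020 × 0.4917 / 0.3999 = 24.8%. With k = 3, g = 13.9%. In MDS, g = 55.2% (k = 2) and 42.9% (k = 3).

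True survival in the arm is 0.9 S + 0.1 g:

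- AML: 42.9% (k = 2), 41.8% (k = 3)
- MDS: 69.6% (k = 2), 68.3% (k = 3)

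If subjects are censored on the day of exit (c = 0), everyone still observed has hazard λ, so Kaplan-Meier returns S. If contact continues for c months, the observed hazard at time t is λ[a(t) + k b(t)] / [a(t) + b(t)]. Here a(t) is the share at risk who have not exited and b(t) is the share who have exited but are still in contact. Integrating this over 12 months gives the Kaplan-Meier value. The overstatement is Kaplan-Meier minus truth, in percentage points:

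| Last contact after exit | AML, k = 2 to 3 | MDS, k = 2 to 3 |
|---|---|---|
| 0 months | 2.0 to 3.1 | 1.6 to 2.8 |
| 1 month | 1.7 to 2.5 | 1.4 to 2.4 |
| 3 months | 1.2 to 1.6 | 1.0 to 1.7 |

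The 1-month and 3-month rows roughly match the safety visits 28 days after azacitidine and 90 days after durvalumab. With k = 1 the overstatement is zero in every row.

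**Step 3: scale.** With about 55 (AML) or 36 (MDS) subjects per arm, the binomial standard error of a difference in 12-month OS is √[2S(1−S)/n]: about 9.5 points in AML and 10.7 in MDS. The illustrated bias is under one third of that.

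**The case against.** The best defence is that 11.2 lists sufficient reasons without saying that survival contact ends, while the sections that govern follow-up are consistent and require it to continue. A careful site would keep calling. This makes the harm conditional. It does not remove the conflict, because SAP 6 describes a study exit as the end of visits and participation.

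Several stronger readings are tempting, and the documents do not support them.

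- **OS is censored at the toxicity.** A reader might infer this, but SAP 10.2 censors at last contact or last known alive, and a known death counts as an event whatever its cause. The safety visits usually move the date later, which lowers the illustrated bias.
- **Late safety data are lost.** Protocol 10.2.6 requires unresolved SAEs to be followed after participation ends. Protocol 10.1 and 10.5 keep suspected-related SAEs reportable at any later time.
- **AML-transformation data are lost.** Protocol 6.6.2 and 10.7.1 keep transformation reportable, and an adverse event is not among their end points. For both kinds of event, only the scheduled prompt from the 3-monthly contact would be lost.
- **The SAP authorises the exit.** SAP 6 tabulates a reason collected on the CRF. The permission comes from Protocol 11.2.

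It is also fair to say that the exit rate, its timing and the hazard ratio are all assumed, that OS is a secondary endpoint for which the study was not sized, and that the illustrated bias is small beside sampling error. All of that stands. It limits the weight of the point, but it is no reason to leave the lists in conflict when correcting them is simple.

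One might also say that the other category in 3.2.4 could absorb an adverse event. A residual category does not reconcile two explicit lists, but it does mean that deleting the named item alone would leave the route open.

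**Conclusion.** The contradiction is established from the text alone: Protocol 11.2 and SAP 6 on one side, Protocol 3.2.4, 3.2.3.2, 6.7.7, 6.15 and 7.2.1.4 on the other. Its possible effect is limited to OS and one-year survival, and to the scheduled prompt for transformation, subsequent therapy and late events. Overall response rate is unaffected.

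The size cannot be fixed from the documents. On the stated assumptions, 10% exits in one arm would overstate its 12-month OS by about 1.2 to 3.1 points (AML) or 1.0 to 2.8 points (MDS). The figure is zero if risk does not rise after exit. To the extent that exits and later risk are alike in both arms, the bias cancels from the comparison. A between-arm bias is therefore possible but not shown. The point is a worthwhile correction to secondary-endpoint follow-up and does not threaten the trial's main conclusion.

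**What to change.** Reconcile Protocol 11.2, SAP 6 and the CRF study-exit list with Protocol 3.2.4:

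1. Remove adverse event as a reason for leaving the study in all three places. State in 11.2 that it is a treatment-discontinuation reason only, as listed in 11.1.
2. State that neither an adverse event nor an entry under other that describes one ends the survival, subsequent-therapy and transformation contacts, unless the subject withdraws consent to follow-up. Without this, the other category leaves the same exit open.
3. Before the OS analysis, query the vital status of any subject already coded as leaving the study for an adverse event.

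The change concerns data collection and leaves decisions about treatment as they are. It costs one list item and one or two sentences in the protocol and SAP, one CRF option, and queries on any subjects already affected. The telephone contacts are already required.
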